### 14.2. Variables

| Data file, identifier patient_display_id_full | Notes   | Variable name | Variable label                                 | Variable level | Nominal values |
|---|---|---------------|--|----------------|----------------|
|   |   |               |  |                |                |
| AE evaluation                                 | sorted by patient_display_id_full and AESTDT and removed duplicates | AERELPET      | Adverse event is relevant for primary endpoint | nominal        | Yes
No      |

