7.2 Endpoints and hypotheses

7.2.1 Primary endpoint and hypothesis

SADE-free rate until the 3-month follow-up

A primary endpoint is an SADE (see definition in section 18) that is possibly, probably or causally related to the BIOMONITOR III, the Incision Tool or the Insertion Tool, or the insertion procedure, which occurs before the 3-month follow-up.

SADEs will be adjudicated by an internal adjudication board, whereby the seriousness and device relatedness will be re-examined. If any amply documented external physical influence (e.g. accident, sport) or medical AE caused the SADE, it does not contribute to this endpoint. SADEs that occur later than the 3-month follow-up, and SADEs with onset date later than 105 days after insertion procedure (3 months defined as 91 days after implantation + 14 days would still be in accordance to the CIP) in case the 3-month follow-up was not conducted or conducted outside the specified time interval, do not contribute to this endpoint.

The parameter of interest p_{SADE} is the SADE free rate, which will be calculated by

$$1 - \frac{\text{Number of patients with one or more primary endpoint until the 3 months FU}}{\text{Number of patients at the 3 months FU or with primary endpoint}}$$

in percent. The period of observation starts with the insertion of the BIOMONITOR III and takes until the 3-month follow-up.

It is expected, that the SADE-free rate will be significantly above 90%. Therefore the corresponding hypotheses definitions are:

Null hypothesis:

$$H_0 : p_{SADE} \leq 90\%$$

Alternative hypothesis:

$$H_A : p_{SADE} > 90\%$$

The following patients are not included in the analysis set for this endpoint:

- Patients without SADE, prematurely terminated before the time window for the 3-month follow-up, i.e. less than 77 days after insertion procedure (3 months defined as 91 days after implantation – 14 days would still be in accordance to the CIP).

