8.1.3 Selection of measurements for endpoints

For the primary endpoint, the SADE-free rate will be assessed by collecting and evaluating adverse events until the 3-month follow-up (see section 7.2.1).

For **secondary endpoint 1**, the R-wave is measured via the programmer. Due to its automatic measurement, this figure unambiguously indicates the device's ability to detect the patient's heart beats. The noise burden for **secondary endpoint 2** is continuously recorded by the device. The value retrieved from the device with the help of the programmer clearly measures the time during which the device is unable to detect the patient's heartbeats.

P-waves are not detected by the device; therefore, the investigators decide whether P-waves are visible in a test ECG. A periodic sECG was chosen as the sample ECG because during arrhythmia, P-waves are often not present. The P-wave visibility (**secondary endpoint 3**) is determined by counting P-waves and QRS-complexes.

For the **secondary endpoint 4** the long-term safety of the BIOMONITOR III system, all SADEs related to the BIOMONITOR III system are collected by the investigators and evaluated by an internal adjudication board as described above. An observation period of 12 months was chosen to significantly extent the monitoring period for safety events beyond the 3 months which are defined for the primary endpoint.

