### 10.1. Analysis set

The number of patients with at least one primary endpoint until the 3 months FU (the numerator) will be determined by assessing the variable "AERELPET" in the "AE evaluation" form. This form is filled by the AE evaluation board and the variable "AERELPET" is set to "Yes" if and only if all conditions defined in 7.2.1 in the CIP are met.

The denominator will be calculated as follows:

1. The number of patients with 3 months FU will be counted by the number of non-missing entries in SVSTDT in the "3 month FU" form.
2. The number of patients with primary endpoint will be calculated as defined above.
3. In case of patients lying in the intersection of both sets, these patients will be counted once.
4. Patients without SADE and termination date less than 77 days after insertion will be disregarded.

Patients who do not attend the 3 months FU, but who have not terminated study participation earlier than 77 days after insertion will be included in the analysis.

For the calculation of the Kaplan-Meier analysis, the following time variables will be used:

1. For patients with at least one primary endpoint: time from insertion to time of first primary endpoint [REDACTED]
2. For patients without primary endpoint: time from insertion to last information available [REDACTED]

For the KM analysis data of all patients is used.

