## 14. Secondary Endpoint4

CIP chapter 7.2.2: Secondary endpoints

SADE-free rate until the 12-month follow-up

The secondary endpoint 4 is the SADE-free rate related to the BIOMONITOR III 12 months after insertion.

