### 14.1. Analysis set

All analyses are performed for the full analysis set.

For the calculation of the Kaplan-Meier analysis, the following time variables will be used:

1. For patients with at least one primary endpoint: time from insertion to time of first primary endpoint (sar\_aestdt\_first).
2. For patients without primary endpoint: time from insertion to last information available (sar\_time\_max).

For the KM analysis data of all patients is used.

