## **14.5. Descriptive Analyses**

A Kaplan-Meier analysis (including Kaplan-Meier plot) will be calculated and the estimation of the SADE-free rate (including two-sided 95% confidence interval) at 12 months (= 365 days) will be given.

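### The 12-month SADE-free rate (secondary endpoint 4) uses an event flag that cannot be Yes after the 3-month visit, so late SADEs are never counted

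*SAP*

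**What the plan says.** Protocol 7.1.2 names long-term safety over 12 months as a secondary objective. SAP 14 defines the matching endpoint: "The secondary endpoint 4 is the SADE-free rate related to the BIOMONITOR III 12 months after insertion". Protocol 8.1.3 gives the reason for it: "An observation period of 12 months was chosen to significantly extent the monitoring period for safety events beyond the 3 months" used for the primary endpoint. The same section has all system-related SADEs collected and passed to the internal adjudication board.

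SAP 14 puts this into practice as follows:

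- **Event variable (14.2):** AERELPET is the one variable listed, labelled "Adverse event is relevant for primary endpoint".
- **Event time (14.1):** time from insertion to the first primary endpoint.
- **Censoring (14.1):** "For patients without primary endpoint: time from insertion to last information available".
- **Estimate (14.5):** a Kaplan-Meier analysis, from which an "estimation of the SADE-free rate (including two-sided 95% confidence interval) at 12 months (= 365 days) will be given".

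AERELPET is defined in SAP 10.1. The adjudication board sets it to Yes "if and only if all conditions defined in 7.2.1 in the CIP are met". Protocol 7.2.1, copied into SAP 10, requires the SADE to occur before the 3-month follow-up. It states that "SADEs that occur later than the 3-month follow-up, and SADEs with onset date later than 105 days after insertion procedure" (the day-105 limit applies when the visit was missed or fell outside its window) do not count.

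**The concern.** The 12-month endpoint takes its events from a flag that carries the 3-month time limit. A patient whose first device-related SADE occurs on day 200 has AERELPET = No, is treated as having no primary endpoint, and is censored as event-free at last information. SAP 14 has no second flag, no exception to the time condition and no window of its own.

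If the SAP is followed, the analysis cannot register any SADE in the part of follow-up that was added to look for late SADEs. The report would give a 12-month SADE-free rate and confidence interval that contain no information on months 4 to 12. The error has one direction: it can only make the device look safer.

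**Working it through.** **Tracing the definition**

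1. SAP 14.5 reads the curve at day 365.
2. An event on that curve requires AERELPET = Yes (SAP 14.2), described in SAP 14.1 as a primary endpoint.
3. AERELPET = Yes requires every condition of Protocol 7.2.1 (SAP 10.1).
4. Protocol 7.2.1 excludes onset after the 3-month visit. That visit is due at 91 ± 14 days, so an in-window visit falls by day 105. If it was missed or out of window, the limit is day 105.
5. The last possible event time is therefore day 105. Days 105 to 365 (260 of 365 days, 71%) cannot contain an event, so S(365) = S(105).

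The SAP 10.3 curve for the primary endpoint is described with the same events and censoring, and is read at day 90. The two readings can differ only through events in days 91 to 105. With the usual Greenwood variance, which adds terms only at event times, the interval at day 365 also equals the one at day 105.

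**The plan's own figures**

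No figure is given for secondary endpoint 4. The sample size (Protocol 11.2) supplies the inputs used below, and it reproduces:

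- Normal approximation: n = [(1.960·√(0.9·0.1) + 1.282·√(0.97·0.03)) / 0.07]² = 132.8, so 133; 133/0.9 gives 148.
- Exact binomial: from n = 141 power stays above 90% (checked to 199). At 141 the test succeeds with at most 7 patients with a SADE, alpha 0.0242, power 93.7%; 141/0.9 gives 157.

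**Illustration of size**

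Inputs: 97% SADE-free at 3 months and 141 patients (Protocol 11.2). Assumptions: late risk q among patients SADE-free at 3 months (not in the documents, so a range is shown) and no drop-out between months 3 and 12.

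- Patients missed = 141 × 0.97 × q = 136.77 × q
- Chance of at least one = 1 − (1 − q)^136.77
- True 12-month rate = 0.97 × (1 − q)
- Overstatement = 0.97 × q

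| q (assumed) | Patients missed | Chance of at least one | True 12-month rate | Rate the SAP targets | Overstatement (points) |
|---|---|---|---|---|---|
| 0.5% | 0.7 | 50% | 96.5% | 97.0% | 0.49 |
| 1% | 1.4 | 75% | 96.0% | 97.0% | 0.97 |
| 2% | 2.7 | 94% | 95.1% | 97.0% | 1.94 |
| 3% | 4.1 | 98% | 94.1% | 97.0% | 2.91 |
| 5% | 6.8 | 99.9% | 92.2% | 97.0% | 4.85 |

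**Worked example (hypothetical data)**

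Take 141 patients with no drop-out, 4 with a SADE by day 80 and 3 more with a first SADE on days 150, 200 and 300. Without censoring before day 365, Kaplan-Meier is the simple proportion.

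- SAP flag: 137/141 = 97.2% at day 105 and 97.2% at day 365.
- Flag running to 12 months: 137/141 = 97.2% at day 105 and 134/141 = 95.0% at day 365.

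**The case against.** Several points can fairly be made for the plan.

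- **Late SADEs are not lost from the study.** They are collected and adjudicated (Protocol 8.1.3), and SAP 15 reports adverse events from the vigilance safety report. This stands: the loss is confined to the secondary endpoint 4 estimate and its interval. But that estimate is the pre-specified endpoint, and the report could list late SADEs beside a rate that counts none of them.
- **No decision depends on it.** The endpoint has no hypothesis (SAP 14.6), everything except the primary analysis is exploratory (SAP 5.3), and pass/fail rests on the primary hypothesis (Protocol 11.5). This also stands: type I error and power are untouched. Exploratory status does not make a 3-month rate a 12-month rate.
- **The effect may be small.** Protocol 5.3 expects most complications early, and the exact 95% interval for 4 SADEs in 141 patients is 92.9% to 99.2%, wider than the shift illustrated for q up to 2%. With no late SADE, nothing changes. But the error always runs one way, and the estimate cannot show whether late SADEs occurred.
- **The board would mark late SADEs Yes in practice.** That would contradict SAP 10.1. It would also harm the primary analysis, whose numerator is taken from AERELPET with no date filter of its own. One flag cannot serve both endpoints.
- **The readable text is incomplete.** The SAP's numbered footnotes are not legible in the public copy, and the time variables in SAP 10.1 are blacked out. The body text of SAP 14.1 still defines events and censoring by the primary endpoint, so the reading does not rest on a footnote.

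The near-identical wording of SAP 10.1 and 14.1 suggests text carried over without adaptation. That explains the error but does not remove it.

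**Conclusion.** The concern holds. As written, SAP 14 cannot estimate secondary endpoint 4: every SADE after the 3-month window is left out of the 12-month rate, and S(365) equals S(105) by construction. This conclusion follows from the definitions alone and needs no assumed figure.

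Only the size rests on assumptions. For a late risk of 0.5% to 2%, the overstatement is about 0.5 to 1.9 percentage points; it grows in proportion to that risk and is zero if no late SADE occurs. The primary endpoint and the pass/fail decision are unaffected. The SAP must be corrected, because a stated secondary objective would otherwise be reported with a figure that does not address it.

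**What to change.** - Add a second adjudicated field to the AE evaluation form, marking relevance for secondary endpoint 4. Set it to Yes for every adjudicated SADE from insertion to the 12-month follow-up that meets the causality conditions of Protocol 7.2.1, without the 3-month and 105-day limits.
- Use this flag and its onset date in SAP 14.1, 14.2 and 14.5 in place of AERELPET and the primary-endpoint wording, for both event time and censoring.
- Leave AERELPET unchanged for the primary endpoint.
- State the causality scope in SAP 14. The endpoint is worded around the device, while Protocol 8.1.3 speaks of the system; the 7.2.1 scope also includes the tools and the insertion procedure.
- While editing, check the event-time variable sar_aestdt_first. SAP 14.1 uses it as the time to the first primary endpoint, but SAP 8 labels it as the onset date of the first AE of any kind.

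**Cost:** SAP wording and one form field. The board already evaluates system-related SADEs for this endpoint (Protocol 8.1.3), and the SAP may be updated before database closure (Protocol 11.8). No new site data and no change in sample size are needed.

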### 14.3. Treatment of Missing and Spurious Data

See general definitions in chapter 5.4

### 14.4. Exclusion of Particular Information

No data are excluded from the analysis from the above analysis set and variables.

## **14.5. Descriptive Analyses**

A Kaplan-Meier analysis (including Kaplan-Meier plot) will be calculated and the estimation of the SADE-free rate (including two-sided 95% confidence interval) at 12 months (= 365 days) will be given.

## **14.6. Hypotheses & Statistical Tests**

There are no pre-defined statistical hypotheses.

## 15. Data of Interest

### CIP chapter .7.5 Further data of interest

Beyond the objectives defined in section 7.1, the study is designed to collect further data of interest. The data on the following topics will be considered 'data of interest' and may be analyzed, as appropriate:

- Demographics
- Medical history
- Indication for ICM
- Usage of incision tool and assessment of incision tool handling
- Assessment of insertion procedure: performance of insertion tool and ease of use (e.g. insertion time, handling and positioning)
- Insertion site
- Insertion success rate
- Wound closure
- Positioning of BIOMONITOR III
- Comfort after wound healing
- Explantation data of BIOMONITOR III
- Additional implantation of BIOMONITOR III
- Serial number of used study devices
- Performance of arrhythmia detection (will be assessed by comparing the BIOMONITOR III detected arrhythmia episodes recorded against a 48-hour Holter ECG, if applicable)
- Syncope and AF: detailed analysis of sensing performance in device-triggered ECG- episodes
- AF burden
  
- Assessment of device programming: individualized programming and re-programming of the device
- Assessment of programmer and programmer software performance
- Remote Assistant III trigger success rate after insertion procedure
- Home Monitoring Data (e.g. transmission success)
- HM workflow efficiency

Assessment of BIOMONITOR III repositioning (if applicable)

- Assessment of BIOMONITOR III migration (if applicable)
- Usability of Patient App (if applicable)
- Information on application of imaging techniques, if applicable (e.g. MRI, mammography)
- Diagnosis and further treatment
- Adverse events and device deficiencies

The topics "demographics", "medical history", and "indication for ICM" are already included in chapter 9.

"Adverse events and device deficiencies" will be reported as provided by the safety report from the vigilance department.

The topics "arrhythmia detection performance", "sensing performance in device triggered ECG episodes" and all analyses based on Home Monitoring data are beyond the scope of this document.

## **15.1. Analysis set**

[figure not shown]
All analyses are performed for the full analysis set.

## **15.2. Variables**

### 15.2.1 Data of interests derived from the insertion CRF only:

This includes the following data of interest:

- Usage of incision tool and assessment of incision tool handling
- Assessment of insertion procedure: performance of insertion tool and ease of use (e.g. insertion time, handling and positioning)
- Insertion site
- Insertion success rate
- Wound closure
- Positioning of BIOMONITOR III
- Remote Assistant III trigger success rate after insertion procedure (for all patients and split by BMI with a cut-off of 30)
- Assessment of BIOMONITOR III repositioning (if applicable)

### 15.2.2 Data of interests derived from the insertion CRF and the FU CRFs:

This includes the following data of interest:

- Assessment of device programming: individualized programming and re-programming of the device
- Assessment of programmer and programmer software performance

### 15.2.3 Data of interests derived from the FU-CRFs:

This includes the following data of interest:

- Comfort after wound healing
- Usability of Patient App (if applicable)
- Information on application of imaging techniques, if applicable (e.g. MRI, mammography)

### 15.2.4 Data of interests derived from the FU-CRFs and the CRF "Deactivation/Explantation" and FU

This includes the following data of interest:

- Assessment of BIOMONITOR III migration (if applicable)

15.2.5 Data of interests derived from the CRFs "Deactivation/Explantation" only

This includes the following data of interest:

- Explantation data of BIOMONITOR III
- Diagnosis and further treatment
- Additional implantation of BIOMONITOR III

In addition to the descriptive reporting of the parameters related to diagnosis and further treatment, a case-by-case listing shall be provided for all patients with a deactivation or explantation. This listing shall contain the following variables:

Baseline CRF:

|          |   |
|----------|---|
| CEINDICM | Primary type of ICM indication                        |
| COINDICM | Specification of other primary type of ICM indication |

Deactivation/Explantation CRF:

|          |   |
|----------|---|
| DXEXREA  | Reason for explantation/deactivation                    |
| PRDGNDT  | Date of diagnosis                                       |
| DUBMDGN  | Did the BIOMONITOR III contribute to this diagnosis?    |
| DUBMDGNA | How did the BIOMONITOR III contribute to the diagnosis? |
| CVARTYP  | Specify arrhythmia type detected                        |
| QSFTRT01 | Ablation procedure                                      |
| QSABPR   | Specify the ablation procedure                          |
| QSFTRT02 | Medication  |
| QSCM01   | Anticoagulation   |
| QSCM02   | Antiarrhythmics   |
| QSCMOTH  | Other   |
| QSFTRT03 | ICD implantation  |
| QSFTRT04 | Pacemaker implantation                                  |
| QSFTRTOT | Other   |
| QSBMU    | Further use of the BIOMONITOR III                       |

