7.5 Further data of interest

Beyond the objectives defined in section 7.1, the study is designed to collect further data of interest. The data on the following topics will be considered 'data of interest' and may be analyzed, as appropriate:

- Demographics
- Medical history
- Indication for ICM
- Usage of incision tool and assessment of incision tool handling
- Assessment of insertion procedure: performance of insertion tool and ease of use (e.g. insertion time, handling and positioning)
- Insertion site
- Insertion success rate
- Wound closure
- Positioning of BIOMONITOR III
- Comfort after wound healing
- Explantation data of BIOMONITOR III
- Additional implantation of BIOMONITOR III
- Serial number of used study devices

- Performance of arrhythmia detection (will be assessed by comparing the BIOMONITOR III detected arrhythmia episodes recorded against a 48-hour Holter ECG, if applicable)
- Syncope and AF: detailed analysis of sensing performance in device-triggered ECG- episodes
- AF burden
- Assessment of device programming: individualized programming and re-programming of the device
- Assessment of programmer and programmer software performance
- Remote Assistant III trigger success rate after insertion procedure
- Home Monitoring Data (e.g. transmission success)
- HM workflow efficiency
- Assessment of BIOMONITOR III repositioning (if applicable)
- Assessment of BIOMONITOR III migration (if applicable)
- Usability of Patient App (if applicable)
- Information on application of imaging techniques, if applicable (e.g. MRI, mammography)
- Diagnosis and further treatment
- Adverse events and device deficiencies

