9.3.1 Procedure after device insertion

The following procedures shall be conducted after insertion:

- Interrogate the newly inserted BIOMONITOR III.
- Perform R-wave measurements (see section 9.5.1).
- Program the BIOMONITOR III according to the clinical indication of the patient.
- Use the indication specific program settings (Go to 'Parameters' – 'Program sets' – 'ProgramConsult', Figure 9) if possible.

[figure not shown]

Figure 9: Use 'ProgramConsult' for indication specific programming.

- **Note:** It is strongly recommended that the high pass signal filter is kept at standard value 0.5 Hz.
- Check that the Home Monitoring function is set to 'ON'.
- Store the electronic procedure data (including final device settings, measurements) of the BIOTRONIK programmer. Provide the programmer data by uploading the PDF-File via the ReportShare-function (see 4.7.1.11 and 9.5.4).
- **Note:** Provide CardioMessenger to the patient and register the patient at the Home Monitoring Service Center (HMSC).
- Activate a periodic sECG recording in the 'Patient profile' tab of the HMSC (Go to 'Remote scheduling', press 'edit' and select 'daily'), Figure 10.

[figure not shown]

Figure 10: Activate daily periodic sECG recording in HMSC.

- Explain to the patient how to use the Remote Assistant III correctly and test the functionality of the Remote Assistant III. Let the patient trigger one sECG recording. If the first attempt was not successful, try to find the reason and try again. Check then if an sECG has been finally stored and report on the eCRF.
- If applicable, provide the Remote Assistant III to the patient for further follow-up.
- Answer questions regarding programmer and programmer software handling and document possible problems¹⁰ regarding device programming.
- Enter data in the insertion eCRFs in the iMedNet EDC database. The use of source data sheet is recommended.
- Document any adverse event or device deficiency during the procedure by using the respective eCRF. Please adhere to the reporting timelines listed in section 18.9.

9.4 1st follow-up, 3- and 12-month follow-up

10 days to 4 weeks after insertion (= 1st follow-up), 3 and 12 months (± 14 days) following the insertion, the patient returns to the investigational site for an in-office assessment of his/her BIOMONITOR III. The following procedures shall be conducted:

- Interrogate the BIOMONITOR III.

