- Inspect the trend values for the R-wave amplitude (see section 9.5.1) and noise burden (see section 9.5.2) at each regular follow-up visit.
- Adjust patient specific program parameters, if applicable. Use the indication specific program settings (Go to 'Parameters' - 'Program sets' - 'ProgramConsult') if possible.
- **1st follow-up:** Program the periodic subcutaneous ECG recording in the 'Patient profile' tab of the HMSC and change cycle duration to 30 days.
- Store the electronic procedure data (including final device settings, measurements) of the BIOTRONIK programmer. Provide the programmer data by uploading the PDF-File via the ReportShare-function (see 4.7.1.11 and 9.5.4).
- P-wave measurements within the HMSC as described in section 9.5.3.
- **1st and 3-month follow-up:** ask the patient to answer the questions regarding the wearing comfort of the BIOMONITOR III
- **1st and 3-month follow-up:** check of insertion location and device migration (if applicable).

¹⁰ Problem means any deficiency of the programmer or software or any adverse events related to the use of the programmer.

- Ask the patient to answer the questions regarding the usability of the Patient App, if applicable.
- Provide further details in case the patient was diagnosed (concerning the medical indication for the BIOMONITOR III).
- Answer questions regarding programmer and programmer software handling and document possible problems¹¹ regarding device programming.
- Answer questions regarding possible examinations by imaging techniques (MRI, mammography).
- Ensure that all source data from the 1st, 3-month and 12-month follow-up are documented, e.g. using a source data sheet which is recommended, and enter data in the respective eCRFs in the iMedNet EDC database.
- Document any adverse event or device deficiency observed during the follow-up by using the respective eCRF. Please adhere to the reporting timelines listed in section 18.

9.5 Description of measurements and other procedures performed at insertion and follow-up visits

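### The SAP takes diagnosis and treatment data only from the Deactivation/Explantation form, so diagnoses recorded at follow-up in patients who keep the device in use are left out of the summary

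*SAP*

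**What the plan says.** Protocol 7.5 names "Diagnosis and further treatment" as one of the further data of interest. Protocol 9.4, which covers all three scheduled follow-ups, tells the site: "Provide further details in case the patient was diagnosed (concerning the medical indication for the BIOMONITOR III". It also tells the site to "enter data in the respective eCRFs in the iMedNet EDC database".

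SAP 15.2 assigns each topic to its source forms. Diagnosis and further treatment stands under "15.2.5 Data of interests derived from the CRFs 'Deactivation/Explantation' only". Every diagnosis and treatment variable named there belongs to the Deactivation/Explantation CRF: date of diagnosis, the device's contribution, arrhythmia type, ablation, medication, and ICD or pacemaker implantation. The same section adds that "a case-by-case listing shall be provided for all patients with a deactivation or explantation".

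SAP 15.2.3, headed "Data of interests derived from the FU-CRFs", covers comfort, the Patient App and imaging. SAP 15.2.2 (insertion and follow-up forms) covers programming and programmer performance. SAP 15.2.4 (follow-up plus Deactivation/Explantation forms) covers migration. None of the three mentions diagnosis.

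**The concern.** The protocol asks for diagnosis information on a wider group of patients than the SAP reads. A patient in whom AF is found after cryptogenic stroke, and whose device goes on being used until month 12, has no reason to receive a Deactivation/Explantation form. Details given at follow-up under Protocol 9.4 would then reach no table or listing.

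The loss would not be random. Diagnoses followed by the end of device use are kept, and diagnoses followed by continued monitoring are dropped. The reported mix of diagnoses and treatments would therefore describe patients whose device use ended, without saying so. The device has no therapeutic function (Protocol 4.5), and improved diagnostic yield is among the benefits cited for this type of device (Protocol 6.1). A selected summary of diagnoses could therefore mislead a reader of the report even though it is descriptive.

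**Working it through.** The documents give no number of diagnoses and no expected yield, so there is no figure to reproduce. The check is a comparison of texts.

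1. **When are diagnoses requested?** Protocol 9.4 applies to the 1st, 3-month and 12-month visits. Items in that list meant for particular visits are labelled with those visits. The diagnosis item carries no label, so it applies at all three.

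2. **When does the form read by the SAP arise?** Protocol 9.7 ties it to explantation or deactivation, and defines deactivation as a permanent decision to stop using the device's information. Under Protocol 8.3.5.4 such patients leave the study once reporting is complete. Protocol 8.3.6 gives later pacemaker or ICD therapy as an example.

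3. **Are patients expected who are diagnosed and keep the device in use?** Yes. Protocol 8.3.2 admits patients under investigation after cryptogenic stroke and patients before or after AF ablation, and Protocol 4.1.3 names management of AF as a main use. The form's own treatment items include ablation and medication, neither of which by itself implies that monitoring has ended.

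4. **Is the topic picked up elsewhere in the SAP?** The introduction to SAP 15 sends demographics, medical history and indication to chapter 9, and sends adverse events and device deficiencies to the safety report. It puts arrhythmia detection performance, sensing in device-triggered episodes and Home Monitoring analyses outside the document. Diagnosis is in none of these groups.

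5. **What happens to a patient without the form?** SAP 5.1 bases relative frequencies on non-missing data, and SAP 5.4 does not impute. The patient drops out of the summary and is not recorded as a negative.

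**Illustration, on assumed figures only.** Let D be the number of patients diagnosed and s the share of them who keep the device in use. Diagnoses omitted = D × s; diagnoses reported = D × (1 − s).

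| Assumed D | s = 25%: reported / omitted | s = 50% | s = 75% |
|---|---|---|---|
| 20 | 15 / 5 | 10 / 10 | 5 / 15 |
| 40 | 30 / 10 | 20 / 20 | 10 / 30 |
| 60 | 45 / 15 | 30 / 30 | 15 / 45 |

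A reader who divided by the planned 157 patients would, for D = 40, obtain 30/157 = 19.1%, 20/157 = 12.7% or 10/157 = 6.4%, against 40/157 = 25.5%. The SAP does not plan that division. The risk of it comes from the layout: SAP 15.1 uses the full analysis set, and the standard tables in SAP 5.1 print the total N beside the non-missing N.

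**The case against.** The strongest case against the point has four parts.

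- **The topic is optional.** Protocol 7.1 puts the focus on safety, and the secondary objectives in 7.1.2 are sensing performance and 12-month safety. Diagnosis is one of many data of interest that need be analysed only where appropriate, with no hypothesis. The protocol promises no estimate of diagnostic yield, and section 4.7.1 says the device itself makes no rhythm diagnosis. This stands, and it limits the priority. It does not remove the mismatch: the SAP chose to report the topic, and SAP 1.1 undertakes to give detailed instructions for all descriptive analyses.

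- **Some evidence is not visible.** The follow-up eCRF fields are not shown, SAP 9.2 is blacked out, and no variable tables appear under SAP 15.2.1 to 15.2.4. Protocol 9.4 does not name the form that holds the diagnosis details, and Table 3 has no diagnosis row. The form described in SAP 15.2.5 also has an item on further use of the device (QSBMU), which fits poorly with a form limited to ended use; the heading may be mislabelled. This stands as uncertainty about the cause. If follow-up fields exist, the SAP leaves them unread. If they do not, the Protocol 9.4 instruction has no evident place to be recorded. Either way the two documents need reconciling.

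- **A listing of explanted and deactivated patients is a coherent product.** This is correct, and the listing should be kept.

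- **A stronger reading is tempting:** that every patient diagnosed with an active device is counted as undiagnosed, so that the report understates yield. The documents do not support this. The SAP has no undiagnosed category, no yield variable and no all-patient denominator for this topic, and it does not turn missing data into a negative. Nor are the data necessarily lost: anything entered at follow-up stays in the database.

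**Conclusion.** The point holds as one of incomplete and selected reporting. Followed as written, SAP 15.2.5 restricts the diagnosis and treatment summary to patients whose device was explanted or permanently no longer used, while Protocol 9.4 asks for diagnosis details at every scheduled follow-up. Patients diagnosed while the device remains in use are omitted, and the summary leans towards diagnoses that end device use.

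The size cannot be derived, because the documents give neither the number of diagnoses nor the share of diagnosed patients who keep the device. The table above shows only how the omission scales. An understated yield would follow only if someone divided the reported count by all patients.

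The conclusion assumes that the heading of SAP 15.2.5 means what it says and that no removed text adds a follow-up source. The primary endpoint, the secondary endpoints, alpha, power and the sample size of 157 are untouched. Priority is minor to moderate.

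**What to change.** - Move diagnosis and further treatment from SAP 15.2.5 to SAP 15.2.4, whose two-source structure already serves migration.
- Name the follow-up variables, including a diagnosis date to set beside PRDGNDT.
- Count each patient once, at the earliest diagnosis date from either source, and report against a stated denominator of inserted patients.
- Keep the listing of explanted and deactivated patients. Add those diagnosed at follow-up to it, or give them a parallel listing.
- If the follow-up eCRFs lack diagnosis fields, reuse the existing items from the Deactivation/Explantation form so that Protocol 9.4 and the SAP agree. A diagnosis row in Protocol Table 3 would make the collection explicit.
- Clarify what QSBMU is for.

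The cost is SAP rewording and a small merge of two data sources. At most, existing CRF items are copied to the follow-up form. No extra visit or procedure is needed.
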